6.5 Measurement of circulating cardiac and vascular inflammatory biomarkers

Plasma and serum samples will be obtained by venipuncture on admission and stored at - 70°C. Plasma probes will be centrifuged for 15 minutes at 10.000 g within 30 minutes of

collection. Probes will be aliquoted and stored at -70°C till analysis. The concentrations of Creactive protein, interleukin 6, vascular cell and intercellular adhesion molecule-1, E-selectin, and monocyte chemoattractant protein-1 will be measured in ethylenediaminetetraacetic acid (EDTA)-plasma at the Oncology Laboratory of the Department of Clinical Therapeutics wellcharacterized enzyme immunoassays. N-terminal pro-B-type natriuretic peptide will be measured with a sandwich immunoassay on an Elecsys 2010 instrument (Roche Diagnostics). Serum cardiac troponin T concentrations will be measured using statndard procedures.

7. Timelines of the study

Vascular measurements and blood collection will be performed at baseline before and 2 hours after dexamethasone and carfilzomib administration. These measurements will be repeated as shown below:

	Before Dexa	After Dexa	Before & after CarD	After CarD	Before & after CarD								
Time points	d -2		d0	d2	d8	d9	d15	d16	C2d1	d2	C3d1	d2	C6d1or 6 months after baseline
Vascular studies	x	X	X†	X	Xt	X	Xt	X	Xt	X	Xt	x	t x
24h ambuatory BF monitoring	×		X*		Х*				X*		X*		X*
Cardiac US	X					1				. 8			X**
Blood for Proteasome activity			x	x	x	x	X?	x	x	x			Xt
Serum collection for cardiac biomarkers	×		×t		×t		×t		×t		x		x

Schedule of assessments

* During 24th of CarD

**Only before C6d1

†2 measurements/ samples at this day

The subjects will be evaluated for AE at all visits.

8. Data presentation and statistical analysis

Data will be presented as mean ± standard deviation (SD). Continuous variables will be tested for normal distribution with the Kolmogorov-Smirnov test. Repeated measures ANOVA will be performed in order to assess significant variations of parameters of interest over time. Linear mixed models analysis will be performed in order to adjust for possible confounders over time. All tests will be two-tailed and statistical significance will be considered for P

values less than 0.05. All statistical analyses will be performed using SPSS version 21 for windows (Chicago, ILL, USA).

9. Safety reporting

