The role of the ubiquitin-proteasome system (UPS) in vascular biology and function is under investigation with controversial results. Over the past decade, accumulating evidence supports the hypothesis of a pathophysiological role of the UPS in the process of atherosclerosis and vascular function. However, the effect of UPS on this process is not well defined. Experimental, clinical and autopsy observational studies have demonstrated that low UPS activity and increased ubiquitin conjugates are associated with unstable coronary, aortic and carotid lesions and vascular aging (11-13). However, experimental studies have yielded contradicting results about the role of UPS inhibition and atherosclerosis. Specifically, UPS inhibition induced deterioration in endothelial function of coronary arteries of hypercholesterolemic pigs and promoted an unstable plague phenotype in apolipoprotein (Apo)E deficient mice (14-15). On the other hand, UPS inhibition in human endothelial cells induced a protective stress response in endothelial cells through up-regulation of antioxidant enzyme expression and of eNOS, an enzyme with pivotal role in endothelial function, suggesting a potential anti-inflammatory and/or anti-oxidant effect (16-18). Similarly, UPS inhibition up-regulated eNOS expression and activity, which was associated with improved renal blood flow (19). Taken together, depending on the environment, dose and duration, cell type and organ studied, proteasome inhibitors can have diverse and broad effects and can act as 'poisons or remedies' in several pathophysiological processes including vascular function and atherosclerosis (20).

In order to clarify this controversial issue, the net effect of UPS inhibition on vascular function and atherosclerosis should be assessed prospectively. To the best of our knowledge, besides animal and autopsy based studies, no clinical human studies have been so far conducted in order to assess UPS inhibition on vascular function. This project will be the first to describe the acute and chronic effect of a proteasome inhibitor on vascular structure and function. Such data would 1. improve our understanding on the pathophysiological pathways linking UPS function and atherosclerosis; 2. provide therapeutic implications on the possible utility of UPS modulation in the prevention and/or treatment of atherosclerosis and 3. improve current knowledge on possible hemodynamic and vascular toxicity of carfilzomib in multiple myeloma.

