4.1 Description of the Study Design

The present study will assess patients with multiple myeloma receiving the proteasome inhibitor carfilzomib (CFZ), in order to investigate, *in vivo*, a wide spectrum of human atherosclerosis stages, cardiovascular risk factors and subclinical atherosclerosis at multiple successive stages in a human model under conditions of global UPS inhibition.

A. Investigation of the role of the UPS inhibition on vascular inflammation and atheromatosis

Circulating biomarkers of vascular inflammation (CRP, IL-6, ICAM-1) and vascular function (endothelial function, arterial wave reflections) and structure (intima media thickness, peripheral atheromatous plaques, plaque echogenicity and arterial stiffness) will be measured at baseline at pre-specified short and long-term time points after treatment. The acute response of vascular function and inflammatory markers to CFZ as well as long term changes in vascular structure after treatment will be assessed. These changes will be examined in comparison to the degree of change in UPS activity by validated techniques.

B. Outline of the clinical significance of carfilzomib therapy in hemodynamic parameters and vascular function and structure

In the same population and under the same design, changes in 24hour ambulatory blood pressure (BP) parameters as well as in vascular parameters as described above will be assessed focusing on time points with significant BP increments and vascular dysfunction. Subsequently, we will examine whether the magnitude of deterioration in these parameters of interest is associated with the degree of UPS activity.

5. Study enrollment and withdrawal

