6.1.3 Sample size

This is an observational study with non interventional design. Sample size calculation is made on the basis of previous data indicating that at least 2% absolute difference in Flow mediated dilatation (FMD) (corresponding to 20-30% relative difference) is considered significant and clinically relevant. With the null hypothesis being that CFZ/Dex therapy is associated with <10% relative difference in FMD and the alternative hypothesis being that a \geq 30% difference is considered as significant, and with an a=0.05, a sample of 40 patients is required for 90% power of detecting these differences (all tests are 2-sided). A dropout rate of 15% is assumed. A total number of 46 patients is thus calculated to be enrolled.

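### Section 8 tests only for overall variation over time; as stated this does not separate the dexamethasone, acute carfilzomib and chronic effects that the protocol promises

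*Protocol*

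**What the plan says.** Section 8 states: "Repeated measures ANOVA will be performed in order to assess significant variations of parameters of interest over time". The next sentence brings in linear mixed models, but only to adjust for possible confounders. Tests are two-sided at 0.05. Section 8 names no before/after factor, no contrast and no reference reading.

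Other sections set out distinct questions:

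- Section 1 promises to describe "the acute and chronic effect of a proteasome inhibitor on vascular structure and function".
- Section 4.1 A: "The acute response of vascular function and inflammatory markers to CFZ as well as long term changes in vascular structure after treatment will be assessed".
- Section 6.1.2 has dexamethasone given 24-48 hours ahead of the first carfilzomib infusion so that each drug's own vascular effect can be assessed.
- Section 6.2.4 (closing paragraph) repeats the vascular measurements at cycle 6 for the chronic effect.
- Section 7: "Vascular measurements and blood collection will be performed at baseline before and 2 hours after dexamethasone and carfilzomib administration". The schedule has columns before and after dexamethasone, then before/after pairs on carfilzomib days, single next-day readings, and C6d1.
- Section 4.1 B says the assessment will concentrate on time points with significant blood pressure rises and vascular dysfunction, and will then relate the size of the deterioration to UPS activity.

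**The concern.** The schedule has two layers, phase (before or 2 hours after dosing) within visit, plus a dexamethasone-only pair. It is built to answer three questions. The stated test asks a fourth: is there any variation over the series? A yes could come from dexamethasone, from a transient post-infusion response, from cumulative change by cycle 6, or from a mixture. The step in Section 4.1 B then lets the observed results decide which time points are examined further. Effects at time points picked this way tend to be overstated, and the nominal 0.05 no longer describes the error rate. The stake is whether the primary vascular results can be reported as acute, chronic and drug-specific effects at all. A secondary stake is the sensitivity of a test that spreads its degrees of freedom over many comparisons.

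**Working it through.** **1. The plan's own figure.** Section 6.1.3 says "a sample of 40 patients is required for 90% power of detecting these differences (all tests are 2-sided". No SD, correlation, time point or test is given, so 40 cannot be derived, only inverted. Read as a paired t-test (an assumption), n = 40 with 90% power implies a standardised paired effect of 0.526. Under compound symmetry the SD of a difference is √2 times the within-patient SD, so this is 0.526 × √2 = 0.74 within-patient SD.

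**2. Number of readings.** In the vascular row of Section 7 there are seven single readings: before and after dexamethasone, d2, d9, d16, C2d2 and C3d2. The paired days are d0, d8, d15, C2d1, C3d1 and, if its mark is the double one, C6d1. That gives 7 + 6 × 2 = 19 readings. If C6d1 is single, it is 7 + 5 × 2 + 1 = 18. Ambulatory pressure is a different series, with six marked points and no before/after pairs.

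**3. Does the overall test separate the effects?** Take n = 40 and 19 readings, with a shift of 0.74 SD at the two C6d1 readings only. The noncentrality is 40 × 0.743² × (2 × 17/19) = 39.6 on (18, 702) df, and power is 0.99. In simulation the first-dose before/after test rejects about 5% of the time, as it should when there is no acute effect. A purely chronic change therefore makes the overall test significant almost surely, and the result is silent on its source.

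**4. Power for an acute effect.** Assumptions: 39 completers (46 × 0.85 = 39.1), 19 readings, compound symmetry, two-sided 0.05, and a shift of d within-patient SD at the six 2-hour readings only.

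- Overall test: noncentrality 39 × d² × (6 × 13/19) = 160.1 d² on (18, 684) df.
- Mean of six (2 h minus before) differences, with variance 2/6 of the within-patient variance: noncentrality 39 × 3 × d² = 117 d² on (1, 38) df.

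| d | Noncentrality, overall / contrast | Power, overall | Power, contrast |
|---|---|---|---|
| 0.20 | 6.40 / 4.68 | 25.6% | 55.9% |
| 0.25 | 10.01 / 7.31 | 41.3% | 75.0% |
| 0.30 | 14.41 / 10.53 | 60.1% | 88.5% |
| 0.40 | 25.62 / 18.72 | 89.9% | 98.8% |
| 0.50 | 40.03 / 29.25 | 99.1% | above 99.9% |
| 0.74 | 87.67 / 64.07 | about 100% | about 100% |

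Sensitivity at d = 0.20, 0.25 and 0.30:

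- 18 readings and five pairs: 23, 37 and 54% overall against 49, 67 and 82% for the contrast.
- Greenhouse-Geisser epsilon 0.7: the overall test falls to 21, 33 and 49%.
- Contrast tested at 0.025: 44.1, 64.5 and 81.5%.

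**5. Power for a chronic effect.** With both C6d1 readings shifted by 0.5 SD, the overall test has noncentrality 39 × 0.25 × (2 × 17/19) = 17.4 and power 71%. The single difference, C6d1 pre-dose minus d-2, has noncentrality 39 × 0.25/2 = 4.9 and power 58%. The chronic contrast gains interpretability, not power.

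**The case against.** The strongest reply is that Section 8 is short and open. It does not say that one ANOVA will span every vascular reading, or that only an overall F will be reported. Repeated measures ANOVA can carry two within-patient factors and planned contrasts, and so can the mixed model that Section 8 already names. Contrasts are often left to a statistical analysis plan, which may exist. A reader might infer that the planned methods are incapable of separating acute from chronic change; the text does not support that. It supports only that, as stated, they are not directed to do so.

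A reader might also infer that the plan halves the power for the acute effect. That is not a general result. It holds roughly for assumed shifts of 0.20-0.25 SD, is nearer a third at 0.30, and has gone at the 0.74 SD implied by 40 patients under a paired test. Nor does the Section 7 sentence on baseline show that readings before and after each drug will be pooled, since the schedule labels them separately. Finally, averaging the acute change over all carfilzomib days mixes the two dose levels in Section 6.1.2 and could hide a dose-related or fading response.

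These points limit the claim but do not remove it. The protocol itself assigns the time question to a test of overall variation and confines the mixed model to confounders, while posing three separate questions elsewhere. It also fixes a results-driven choice of time points in Section 4.1 B. That is a mismatch between stated aims and stated analysis, not merely detail left for later.

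**Conclusion.** The point holds as a mismatch that should be corrected. Followed as written, the overall time test answers none of the acute, chronic or dexamethasone-only questions, and the follow-up in Section 4.1 B is chosen from the data. This conclusion rests on the text alone and needs no numerical assumption. It concerns the vascular function series, not ambulatory pressure.

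The power argument is secondary and conditional. It rests on assumed small shifts recurring after each dose, compound symmetry and 39 completers, and it applies to the acute contrast only. Because the protocol gives no SD for FMD, it cannot be said where on that range the study lies.

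**What to change.** In Section 8, make the mixed model the main analysis of the vascular function series, with phase (before / 2 h after), visit and phase-by-visit terms. Name these contrasts and their order:

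1. Acute: 2 h after minus before on the carfilzomib days, with the first, lower-dose day also shown separately.
2. Chronic: C6d1 pre-dose minus the d-2 reading before dexamethasone.
3. Dexamethasone only: d-2 after minus before.

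Use the d0 pre-dose reading only as the reference for that day's acute change. Keep the overall time test as descriptive, and state in Section 4.1 B that the link with UPS activity is examined for these contrasts rather than for time points selected by significance. Since Section 6.1.2 also schedules dexamethasone on carfilzomib days, label contrast 1 as the response to the dosing day wherever both drugs are given. Confirm in Section 7 whether C6d1 is single or double.

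The cost is wording, with no new visits or data. The downside is that several named tests replace one, so they must be tested in a fixed order or share alpha. At 0.025, the acute contrast at 0.20 SD drops from 55.9% to 44.1% power, still above the 25.6% of the overall test.

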9.1 Adverse Events Definitions

An adverse event (AE) is any untoward medical occurrence in a subject administered a medicinal product and that does not necessarily have a causal relationship with this treatment. An AE therefore can be any unfavorable and unintended sign (including laboratory finding), symptom or disease temporally associated with participation in a study, whether or not considered drug-related. In addition to new events, any increase in the severity or frequency of a pre-existing condition that occurs after the subject signs a consent form for participation is considered an AE. This includes any side effect, injury, toxicity, or sensitivity reaction.

The definition of an AE includes:

- Worsening of a pre-existing condition
- Events occurring from a medication error or overdose of a product(s), whether accidental or intentional
- Events occurring from abuse of a product(s)
- Events associated with the discontinuation of the use of a product(s), (eg, appearance of new symptoms)
- Any lack or loss of intended effect of the product(s)

Any condition, laboratory abnormality, or physical finding with an onset date prior to the subject signing consent for study participation is considered to be pre-existing in nature and part of the subject's medical history.

9.2 Causality

Using the following criteria, the relationship of the AE to a drug should be assessed as follows:

- Yes: The event is suspected to be related if:
 - there is a clinically plausible time sequence between onset of the AE and administration of treatment; and/or
 - there is a biologically plausible mechanism for the treatment to cause or contribute to the AE; and/or
 - the event responds to withdrawal of the medication (dechallenge) and/or recurs with rechallenge (when clinically feasible); and/or
 - the AE cannot be reasonably attributed to concurrent/underlying illness, other drugs, or procedures

- No:
 - the AE is more likely to be explained by the subject's clinical state, underlying disease, concomitant medication, study or non-study procedure; and/or
 - the time of occurrence of the AE is not reasonably related to administration of treatment; and/or
 - the event is unlikely to be related to the treatment(s)

9.3 Definition of Adverse Drug Reactions (ADRs)

AEs that are considered related to a product are classified as adverse drug reactions (ADRs).

9.3.1 Definition of Serious Adverse Events

A serious adverse event (SAE) is any AE as defined above that also:

- is fatal
- is life threatening (places the patient at immediate risk of death)
- requires in-patient hospitalization or prolongation of existing hospitalization
- results in persistent or significant disability/incapacity
- is a congenital anomaly/birth defect
- is an "other significant medical hazard" that does not meet any of the above criteria

A hospitalization meeting the regulatory definition for "serious" is any in-patient hospital admission that includes a minimum of an overnight stay in a healthcare facility. "Other significant medical hazards" refer to important medical events that may not be immediately life-threatening or result in death or hospitalization, but may jeopardize the patient or may require intervention to prevent one of the other outcomes listed in the definition above.

Any death occurring within 30 days of the subject receiving study drug, regardless of the subject having discontinued from the study must be reported to the Sponsor as an SAE.

9.3.2 Definition of Serious Adverse Drug Reactions (SADRs)

SAEs that are considered related to any product are classified as serious adverse drug reactions (SADRs).

9.3.3 Definition of Special Situations

Special Situations include:

- Medication errors, overdose, misuse, or abuse, whether accidental or intentional, involving any product, regardless of whether associated with an AE, SAE, ADR and/or SADR
- Pregnancy and lactation exposure regardless of whether associated with an AE, SAE, ADR and/or SADR

Transmission of infectious agents regardless of whether associated with an AE, SAE,ADR and/or SADR

Reports of uses outside the terms for authorized use of the product including off label use when associated with an AE, SAE, ADR and/or SADR

Occupational exposure

Product complaints

9.4 Adverse Events Reporting Procedures

All AEs (e.g., any new event or worsening in severity or frequency of a pre-existing condition or laboratory finding) with an onset date after the subject signs consent for study participation must be documented on the appropriate summary. Details of the event must include severity, relationship to study drug, duration, action taken, and outcomeAdverse drug reactions (ADRs) will be recorded on the appropriate form.

All AEs that are considered related to study drug must be followed to resolution or stabilization if improvement is not expected.

AEs should be reported from the time the subject signs consent through 30 days post-last dose of study drug or initiation of a new anti-cancer therapy, whichever occurs first. In addition, the Investigators should report any AE that may occur after this time period that is believed to have a reasonable possibility of being associated with study drug. AEs which completely resolve and then recur should be recorded as a new AE. For subjects who complete the end of study visit less than 30 days following their last dose of study drug, a follow up of ongoing AEs should be attempted by telephone, and documented in the subject's source. AEs continuing at 30 days post-last dose should have a comment in the source by the Investigators that the event has stabilized or is not expected to improve.

The Sponsor is responsible for evaluating all AEs, obtaining supporting documents, and determining that documentation of the event is adequate.

All Grade 3 and 4 laboratory abnormalities must be recorded as AEs on the CRF. Grade 1 and 2 abnormalities should only be recorded if they require treatment or are otherwise considered clinically significant by the Investigator.

9.4 Serious Adverse Event Reporting and Documentation Requirements

All SAEs occurring from the time that the subject signs consent for study participation through 30 days after the last administered dose of treatment will be reported. SAEs must be reported by Investigators to the Sponsor's designated point of contact by fax within 24 hours after the event was known to the investigator, using the SAE report form provided. This initial report should contain a minimum amount of information regarding the event, associated

treatment and patient identification, as described in the detail in the instructions. All SAEs regardless of relationship to study drug must be followed to resolution or to stabilization if improvement or resolution is not expected.

If a subject is permanently withdrawn from the study because of a SAE, this information must be included in the initial or follow-up SAE report as well as the appropriate form for Study Discontinuation.

The Sponsor and/or the Investigators are responsible for notifying the appropriate Regulatory Agencies, when required, and in accordance with applicable laws and regulations of any Expedited Safety Reports. Generally, these are all SAEs that are judged to be unexpected and related to study drug(s), as specified in ICH E2B guidelines. The Sponsor and/or Investigators are also responsible for notifying the Institutional Review Board (IRB) or Independent Ethics Committee (IEC) as applicable and in accordance with local regulations, of all SAEs.

The Sponsor is responsible to create a Final study Report (FSR) of the overall conduct of the specific study for distribution to the relevant EC(s) and Regulatory Agencies. The FSR will also be provided to Amgen at the end of the study.

